## **Background**

Accurately quantifying food intake is vital to promoting health and reducing chronic disease risk. Food intake encompasses energy intake, nutrient intake (macronutrients, micronutrients, vitamins, minerals), and intake of various food groups (e.g., fruits, vegetables), and thus reflects the nutritional status of individuals. Nutrition affects disease risk, including risk of developing obesity, diabetes, and cancer, all of which negatively affect the United States (U.S). Nonetheless, accurate assessment of food and nutrient intake has remained challenging, despite an improvement in methods. Self-report methods, namely food records, are a mainstay of nutritional epidemiology research, with food recall being another popular method. These methods rely on the participant to accurately estimate portion size and, for food recall, remember what was consumed. The accuracy of these methods have been questioned and the problems with human recall have been comprehensively outlined. As a result, there remains a significant need for methods that are sufficiently accurate to provide researchers with good outcome data and to guide health promotion efforts.

The PortionSize™ app was designed by our laboratory to overcome the limitations outlined above, and to guide users to follow specific diets. PortionSize™ relies on users capturing images of their food selection and waste. Food intake data are immediately provided since the user relies on built in tools, including templates, to estimate portion size. However, despite promising early indications, the PortionSize™ app has yet to be validated. Determining the accuracy and reliability of PortionSize™ is vital before the app can be used by people to obtain immediate feedback about their food intake. We accordingly aim to test the reliability and validity of PortionSize™ in a semi-controlled free-living environment using food provision. We will also test the reliability and validity of the MyFitnessPal app in a semi-controlled free-living environment. The accuracy of the apps will also be compared to each other.

## Methods

### Study Design

We will recruit adults to use the PortionSize™ app and the MyFitnessPal apps in free-living conditions, where participants will consume pre-weighed food from a cooler, which provides a test of nutrient intake in free-living conditions. Participants will consume pre-prepared and pre-weighed foods from a cooler for two non-consecutive three-day periods that are separated by approximately one week. In a within subjects and randomized, counterbalanced design, participants will use PortionSize™ during one three-day period and MyFitnessPal during the other period. Following our previous methods, participants will pick up a cooler in the morning and, at approximately the same time, return the cooler from the previous day, allowing us to weigh food waste (i.e., determine food intake since the foods were weighed when they were put in the cooler). This procedure allows us to test the accuracy of the apps at measuring energy and nutrient intake in free-living conditions. Participants will be trained in our clinic/laboratory to use the apps following the procedures of Study 1.

### Participants and Recruitment

We will recruit 45 adults (approximately equal proportion of men and women) who will be randomly assigned to use PortionSize™ or MyFitnessPal. We expect to enroll an approximately equal number of participants with body mass indexes (BMI; kg/m^2) between 18.5 to 25, 25 to 30, and 30 – 50kg/m^2. Recruitment will be stratified based on sex and body mass index.

- Inclusion criteria include:
  - Male or female, age 18-62 years
  - Body mass index (BMI) 18.5-50 kg/m^2
  - Subjects who are capable of giving informed consent and complying with all study procedures/requirements.
  - Ownership of an iPhone model 6s or later, which the participant is willing to use for the study
  - Access to Apple ID, password, and email address and willing to use them during the study
  - Willing to use data and any accompanying charges as part of study participation
  - Willing to complete all study procedures and adhere to study visit timelines
  - Willing to be re-contacted for future research and/or follow-up
- Exclusion criteria include
  - Active cancer diagnosis (excluding some melanomas)
  - Have been 6-month weight unstable (gain/loss >10 lbs in last 6 months)
  - Undergoing weight loss treatment

- PBRC employee, as previous reviewers argued that they are not representative of the community
- Women who are currently pregnant or breastfeeding (self-reported)
- Diagnosed with an uncontrolled thyroid disorder (controlled = 3 months of medication)
- Have had or plan to have weight loss surgery (*gastric band removal may be allowed at PI discretion*)
- Allergic to or unwilling to eat study foods provided (*exceptions made at the discretion of the PI*)
- Consume >28 alcoholic beverages per week
- Anyone severely immunocompromised
- Any condition or circumstance that in the judgement of the PI could interfere with study participation

## Procedures

### ***Screening visit***

At the screening visit, an individual or group presentation related to study procedures will be presented. For participants interested in participating thereafter, a written informed consent will be obtained. Once consented, the following will occur:

- Completion of study questionnaires including the Lifestyle and Demographics Questionnaire and a Dietary Screening Questionnaire
- Anthropometrics: height, weight (non-metabolic) and BMI
- Determine eligibility to proceed with Day 0.

### ***Testing Period 1 & Period 2***

Eligible participants who choose to enroll will complete 2 testing periods (Period 1 and Period 2) where they will be provided with prepared foods from the Metabolic Kitchen to consume over 3 days. Once Period 1 is complete, participants will have a washout period before starting Period 2. Participants will be randomized to use either the PortionSize™ app or MyFitnessPal app for Period 1 or Period 2. Period 1 will include a baseline visit to randomize the participant to app order and to train the participant how to use the app that they are to use first. Period 2 will include a Day 0 for app training. Each period will have the following visit days: Day 1, 2, 3, and 4.

Visits for each period are ideally consecutive days. For example, Day 1 is +1 day from Baseline/Day 0, Day 2 is +1 day from Day 1, etc. This is not possible, however, for participants whose data collection spans a weekend or a holiday, for example. Additionally, circumstances may arise that prohibit participants' or the Center's ability to collect data across 4 consecutive days (inclusive of the run-in day and Day 4 when participants return their last cooler). Thus, efforts will be made for Day 1 to

occur the day after Baseline/Day 0, though the PIs may approve changes to this schedule if it is not possible due to an unforeseen event. Similarly, the PIs may approve the collection of data on non-consecutive days between Days 1 and 2, and 2 and 3 due to unforeseen events, illness, holidays, etc. In rare cases where many days elapse between either Day 1 and 2, or 2 and 3, the PIs may request that the participant complete an abbreviated booster training and run-in for the app being used during that period. In no cases shall more than 14 days elapse between days of data collection. Lastly, in cases where Days 1 and 2, and/or 2 and 3, are not sequential, up to two additional visits to the Center are possible since the participant cannot drop off and pick up their next cooler in the same visit.

After the completion of Period 1, a washout of approximately 1 week will occur before initiating Period 2. The washout period may be expanded up to 30-45 days as needed for scheduling and unexpected circumstances.

Food pick-up and drop-off visits can be repeated at the PI's discretion to provide participants and staff flexibility. Should extenuating circumstances occur, this will allow for proper data collection and quality in the face of unforeseen events.

### ***Baseline (and Day 0)***

Participants will attend an in-person visit at Pennington for Baseline, which occurs during Period 1, to be randomized and trained how to use the app that they will use first. During Day 0, which occurs during Period 2, participants will be trained to use the app that they will use second. These visits will last ~45 to 60 minutes. The training will teach participants how to report food intake and estimate portion size per our standard procedures. Participants will receive training by study staff members on the app that they will use for that period. That is, individuals randomized to use PortionSize™ first will be trained on PortionSize™, whereas those randomized to use MyFitnessPal first will be trained on MyFitnessPal. This first day is usually a partial day of data collection and will serve as a run-in/familiarization period for the participants, during which they will be instructed to use the app for the remainder of the day. These data will not be analyzed as part of the 3-day use period.

### ***Day 1***

Participants will return to the lab before breakfast in the morning to be weighed (non-metabolic) and be provided with the first cooler of food to consume for the remainder of the day. The coolers will contain about 1.3 times the participant's overall estimated energy needs, with ~20%, 30%, 40%, and 10% of energy provided as breakfast, lunch, dinner, and snacks, respectively. Staff will attempt to provide a day's worth of food that reflects 50% carbohydrate, 20% protein, and 30% fat (+/- 5%). The Mifflin St. Jeor Equation will be used to calculate basal metabolic rate (BMR), and total energy requirements will be calculated by multiplying BMR by an activity factor of 1.5. This value then will be multiplied by 1.3 to provide 30% more energy than the person requires. Participants will be instructed to only consume foods and beverages (with the

exception of water and non-caloric beverages such as black coffee or plain tea) from the cooler, but they can eat/drink as much or as little as they wish. Participants who report drinking diet, regular sodas, or sweet teas will be provided with their preferred beverage in their cooler, and efforts will be made to provide these beverages in typical store-bought containers (e.g., 12-ounce cans). All food and beverage items will be pre-weighed and weighed immediately upon return per our previous methods. We may include dietary supplement(s) on certain days, though the supplement may vary among participants (e.g., multivitamin, energy bar or shake, etc.).

This visit will last approximately 15-30 minutes.

### **Day 2**

Participants will return to the lab before breakfast in the morning to be weighed (non-metabolic) and to return their cooler from Day 1. They will then pick up a new cooler containing their food and beverages for Day 2. The cooler content and procedures are the same as described above though the menus of foods in the cooler may differ each day. This visit will last approximately 15-30 minutes.

### **Day 3**

Participants will return to the lab before breakfast in the morning to be weighed (non-metabolic) to return their cooler from Day 2. They will then pick up a new cooler containing their food and beverages for Day 3. The cooler content and procedures are the same as described above though the menus or foods in the cooler may differ each day. This visit will last approximately 15-30 minutes.

### **Day 4**

After 3 days of study food tracking, participants will have their weight measured a final time and return the cooler to the laboratory. They will then complete the following questionnaires:

- The Computer System Usability Questionnaire (CSUQ) for MyFitnessPal or PortionSize™ (the CSUQ that is completed will correspond to the app used during that period). The CSUQ is a standardized, reliable, and valid questionnaire originally designed to evaluate computer programs that has been used to quantify the usability of mobile phone apps.
- The PortionSize™ User Satisfaction Survey or the MyFitnessPal User Satisfaction Survey (the survey that is completed will correspond to the app used during that period).
- PortionSize and MyFitnessPal-specific Dietary Health Questionnaires (DHQ III) are modified such that participants will report the presence of vitamins and supplements during the days of food provision. Thus, only those items (vitamins and supplements) of the DHQ-III will be administered, and the instructions will ask participants to note if those items were present in the coolers.

- Period 2 only, the User Preference Survey.

The visit will last approximately 30-60 minutes for Period 2 with the addition of the Preference Survey.

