### Outcome measures

The **primary analyses** assessing equivalence between PortionSize™ and the criterion measure (and MyFitnessPal and the criterion measures) will rely on equivalence testing using the Two One-side T-test (TOST) method. The null hypothesis of an equivalence tests is that the means are nonequivalent, i.e., the confidence interval of the mean of the test condition exceeds the pre-specified error bound. The alternative hypothesis is that the means are equivalent, and the mean difference between the experimental method and gold standard is hypothesized to be zero. Differences in error from PortionSize™ compared to error from MyFitnessPal will be assessed using dependent samples t-tests, with error calculated as the difference between each experimental method and the criterion variable (e.g., energy intake values from PortionSize™ minus energy intake values from weighed foods). These procedures will also produce results indicating if the error from each method differs from zero.

Subsequent regression-based **exploratory analyses** will determine if error from the apps varies by body mass (kg, BMI), age, or sex; and will evaluate differences in user satisfaction between the apps. Bland-Altman analysis will be used to test for differences in error variance over levels of the variable being measured (e.g., food intake).

Endpoints will be:

- Energy intake (kcal)
- User satisfaction and usability of the apps
- Nutrients (e.g., fat, carbohydrate, and protein as grams and percent energy from each macronutrient) and food groups (PortionSize™ only since it has the ability to provide output in food groups due to the link with the FNDDS database).

Other exploratory endpoints include human rater analysis of captured food images and the modified Dietary History Questionnaire III (DHQIII) as comparators for food and possible dietary supplement intake.

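### As described, the modified DHQ-III records whether supplements were in the cooler, so it cannot be the comparator for food and supplement intake that Outcome measures makes it

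*Combined protocol and SAP*

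**What the plan says.** Three parts of the combined protocol and SAP bear on this.

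- **Day 1 (what is provided).** Supplements are optional and not uniform: "We may include dietary supplement(s) on certain days, though the supplement may vary among participants". The examples given are a multivitamin and an energy bar or shake. Of the cooler contents in general, participants are told that "they can eat/drink as much or as little as they wish". Weighing is described as follows: "All food and beverage items will be pre-weighed and weighed immediately upon return per our previous methods". Supplements are not named in that sentence.
- **Day 4 (what is asked).** The DHQ-III is modified so that "participants will report the presence of vitamins and supplements during the days of food provision". The item set is restricted, in that "only those items (vitamins and supplements) of the DHQ-III will be administered". On how participants are to answer, the section states that "the instructions will ask participants to note if those items were present in the coolers".
- **Outcome measures (what it is for).** "Other exploratory endpoints include human rater analysis of captured food images", and the same sentence adds "the modified Dietary History Questionnaire III (DHQIII) as comparators for food and possible dietary supplement intake".

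The Schedule of procedures places the questionnaire on Day 4, once for each app. No section says how the answers will be scored, converted to intake or analysed.

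**The concern.** A comparator has to measure the quantity it is compared with. The endpoint sentence speaks of intake, while the Day 4 instruction speaks of presence. In a study where participants choose what to consume from a deliberately generous cooler, these are different quantities.

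The food half of the sentence has a similar problem: an instrument reduced to vitamin and supplement items holds no information on food.

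At stake is whether the trial can say anything from this questionnaire about how well either app captures supplement intake. The timing makes it worth settling before data collection. If consumption is not asked on Day 4, it cannot be recovered reliably afterwards, whereas a missing analysis detail could still be written later.

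**Working it through.** The documents state no figure for this endpoint, and the point depends on no alpha, SD, margin or sample size, so there is nothing to recompute. The check is a comparison of the texts.

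**Step 1. What a correct presence answer can tell us.** For one supplement on one day there are three possible states.

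| State | True intake | Correct presence answer | Kitchen's knowledge at packing |
|---|---|---|---|
| Not packed | none | no | not packed |
| Packed and taken | some | yes | packed |
| Packed and left | none | yes | packed |

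The second and third rows differ in intake but not in the presence answer. Even a participant with perfect recall gives an answer that cannot separate them. The presence column also matches the packing column throughout. The question can therefore test whether participants noticed and remembered the supplement, but it adds nothing on whether they took it.

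**Step 2. Whether the third row can occur.** It can. Day 1 leaves consumption to the participant and exempts no cooler item. The documents do not say how often a supplement would be left.

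**Step 3. Whether days or amounts are recorded.** Supplements may be included on certain days only, and one questionnaire covers a three-day period. The description on Day 4 mentions neither the number of days nor an amount.

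**Step 4. Food.** Day 4 retains only vitamin and supplement items. The Outcome measures sentence can be made to work only by reading it as image rating for food and DHQ-III for supplements. That reading removes the food problem but leaves the gap between presence and intake in Steps 1 and 2.

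**Step 5. Other sources of supplement intake in the plan.**

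- *Image rating.* Named as a second comparator. The Background describes users photographing food selection and waste with PortionSize; no section describes image capture for MyFitnessPal. Images also depend on the user recording the item, so an overlooked supplement may leave no image.
- *Weighing on return.* The sentence covers food and beverage items. A bar or shake plausibly falls under it; a multivitamin pill is not clearly included.

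These sources could supply some information on intake, but neither makes the DHQ-III itself a measure of intake.

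**The case against.** The strongest reply is that this is a labelling slip in a hedged, exploratory sentence. Supplements are only a possibility in the plan, two comparators are named together, and a presence question with a known answer is a coherent test of detection or recall. The questionnaire itself is not reproduced, so the retained items may still ask about frequency or amount, and the cooler instruction may be meant only to restrict answers to study-provided items rather than habitual use.

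Much of this stands. It rules out three stronger conclusions that a reader might draw.

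- *That supplement intake cannot be assessed at all.* The documents do not support this: image rating is a named comparator, and a bar or shake may be weighed on return.
- *That the plan will count a supplement correctly left out of the app as an app error, and so understate app accuracy.* No section defines a score, a capture rate or an agreement statistic between app and DHQ-III. The analysis is unspecified, so no bias is shown.
- *That the extra energy in the cooler, 1.3 times estimated need, indicates how often supplements are left.* It does not. The surplus is a share of energy, and it says nothing about whether a discrete item such as a pill is taken.

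What the reply does not remove is the mismatch itself. Every description of the questionnaire on Day 4 is in terms of presence, none mentions consumption, and Outcome measures assigns it to intake. If the retained items do ask about use, the protocol should say so, because an instruction about presence would then conflict with them.

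**Conclusion.** The point holds in limited form. As Day 4 describes it, the modified DHQ-III measures whether vitamins and supplements were in the cooler, and presence does not establish intake when participants may leave anything unconsumed. Nor can it be a comparator for food on the item set retained.

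The reach is small: one exploratory endpoint. The equivalence tests of each app against weighed intake and the power calculation, which is based on energy intake, do not depend on it. No numerical size can be given, because neither the number of supplement days nor the share left untaken is stated.

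The conclusion assumes that the Day 4 text describes the questionnaire fully. If the instrument already contains a consumption item, the remedy reduces to saying so and stating how that item is used. The point is still worth acting on, since the information has to be collected on Day 4 and the change is cheap.

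**What to change.** 1. **Day 4.** For each vitamin or supplement item, ask whether it was consumed and on how many of the three days. Keep presence in the cooler as a separate item, described as detection.
2. **Day 1.** State that supplements, including pills, are logged when packed and checked on return, and name that record as the criterion for what was provided and consumed. As with weighed food, this takes an item that was not returned as consumed.
3. **Outcome measures.** Limit the DHQ-III's role to supplements, leave food to the image rating, and state how the DHQ-III answers will be compared with the criterion and with each app.

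If the sponsor prefers not to alter the questionnaire, the alternative is to reword Outcome measures so that the endpoint is detection of supplement presence against known cooler contents, with no claim about intake. That resolves the inconsistency but gives up any self-reported intake information.

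The cost of the first route is one or two more questionnaire items and a brief check of returned supplements at a visit that already takes place. The alternative costs only the rewording. Neither adds a visit.

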### Outcome measures

The **primary analyses** assessing equivalence between PortionSize™ and the criterion measure (and MyFitnessPal and the criterion measures) will rely on equivalence testing using the Two One-side T-test (TOST) method. The null hypothesis of an equivalence tests is that the means are nonequivalent, i.e., the confidence interval of the mean of the test condition exceeds the pre-specified error bound. The alternative hypothesis is that the means are equivalent, and the mean difference between the experimental method and gold standard is hypothesized to be zero. Differences in error from PortionSize™ compared to error from MyFitnessPal will be assessed using dependent samples t-tests, with error calculated as the difference between each experimental method and the criterion variable (e.g., energy intake values from PortionSize™ minus energy intake values from weighed foods). These procedures will also produce results indicating if the error from each method differs from zero.

Subsequent regression-based **exploratory analyses** will determine if error from the apps varies by body mass (kg, BMI), age, or sex; and will evaluate differences in user satisfaction between the apps. Bland-Altman analysis will be used to test for differences in error variance over levels of the variable being measured (e.g., food intake).

Endpoints will be:

- Energy intake (kcal)
- User satisfaction and usability of the apps
- Nutrients (e.g., fat, carbohydrate, and protein as grams and percent energy from each macronutrient) and food groups (PortionSize™ only since it has the ability to provide output in food groups due to the link with the FNDDS database).

Other exploratory endpoints include human rater analysis of captured food images and the modified Dietary History Questionnaire III (DHQIII) as comparators for food and possible dietary supplement intake.

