### Power calculation

We expect no more than ~8% drop-out and will recruit at least 45 participants; hence, power analyses were conducted with a sample size of at least 42.

Estimated food intake values from the PortionSize™ and MyFitnessPal apps will be compared to directly weighed values, which serve as the criterion measure. Equivalence tests that follow the Two One-sided T-test (TOST) method will be used

(error reflects the difference between weighed intake and estimates from either PortionSize or MyFitnessPal). Based on a new power analysis and variance estimates from a recently completed pilot study, equivalence is set as within  $\pm$  17.9% of the directly weighed value. The power assumed: 42 participants, energy (kcal) intake as the outcome variable, alpha = 0.05, power  $>0.80$  as acceptable, and mean weighed intake = 2,360 kcal with an SD (difference) = 917 kcal. We will also test for equivalence at the original bound of  $\pm$  9%, as well as a new bound of  $\pm$  14%, though we recognize that these tests will likely be underpowered. Finally, with at least 42 participants completing the PortionSize and MyFitnessPal condition, we have 0.80 power to detect an R^2 of 0.17, which is acceptable as studies with Bland-Altman analysis find that poor methods of measurement frequently have R^2  $>0.16$ .

With 42 participants in each group, power is limited for the tests to examine differences in error between PortionSize™ and MyFitnessPal; therefore, these comparisons are exploratory.

The reliability of each apps' food intake estimates will be quantified with intraclass correlation coefficients (ICCs), and reliability will be supported if the ICC is significant and  $\geq 0.50$ . A power analysis indicates that, with 2 observations per subject, an ICC of 0.54 can be detected with 23 subjects at 80% power. The power analysis was conducted in R software using the 'ICC.Sample.Size' package based on Zou. Regression-based exploratory analyses are powered to detect an R^2 of 0.127 and thus have ample power.

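### Minor improvement: adjust the exploratory PortionSize-versus-MyFitnessPal comparison of error for period, using one named method and analysis set

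*Combined protocol and SAP*

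**What the plan says.** All references are to the combined protocol and SAP.

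- **Study Design** sets up a two-period crossover: "In a within subjects and randomized, counterbalanced design, participants will use PortionSize" in one three-day period and MyFitnessPal in the other.
- **Testing Period 1 & Period 2** states what is randomised: "Period 1 will include a baseline visit to randomize the participant to app order". A washout of about a week follows Period 1 and can be extended.
- **Baseline (and Day 0)** provides training before each period: "The training will teach participants how to report food intake and estimate portion size per our standard procedures". A run-in follows each training, and of the run-in data it says "These data will not be analyzed as part of the 3-day use period".
- **Outcome measures** says that error from PortionSize "compared to error from MyFitnessPal will be assessed using dependent samples t-tests". The same sentence goes on to define the quantity compared: "with error calculated as the difference between each experimental method and the criterion variable". The modifiers of error planned for the regression analyses are body mass, age and sex. Period and order are not listed there or elsewhere.
- **Power calculation** calls the between-app comparison exploratory because its power is limited, although Outcome measures describes the test in its paragraph on the primary analyses.

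**The concern.** The design randomises order, but the one comparison that sets the two periods against each other within a person does not use it. Suppose error changes between Period 1 and Period 2 for both apps alike, for example through practice. A paired t-test then treats that systematic change as random scatter. If completers are unequal by order, part of the change also enters the estimated app difference.

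At stake are a little precision in a comparison that the plan already regards as short of power, and protection of the estimate if dropout falls unevenly on the two orders. Fixing the method in advance also avoids choosing it after the split is known.

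**Working it through.** **The plan's own figure.** Power calculation gives 42 participants, alpha 0.05 and "mean weighed intake = 2,360 kcal with an SD (difference) = 917 kcal". The margin is 0.179 × 2,360 = 422 kcal and the standard error is 917/√42 = 141.5 kcal. Exact TOST power at a true difference of zero is 0.803, so the stated power above 0.80 reproduces. The plan states no power for the between-app comparison.

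**Assumptions not in the documents**
- Period effect π (change in error from Period 1 to Period 2, common to both apps): 100, 200 or 300 kcal. The largest is 13% of 2,360 kcal.
- Error SD of 917 kcal for both apps. The plan does not say which app its figure describes.
- Correlation r between the two apps' errors: 0.5, varied to 0 and 0.7.
- 42 completers, n1 in one order and n2 in the other, N = n1 + n2.

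**Formulas.** The within-person app difference in error has mean δ + π in one order and δ − π in the other, with SD s0 = √(917² + 917² − 2r·917²). This is 917 kcal at r = 0.5, 1,297 at r = 0 and 710 at r = 0.7.
- Unadjusted: variance s0² + π²·(4·n1·n2/N²)·N/(N−1), divided by N for the squared standard error; 41 df (t = 2.0195).
- Adjusted: standard error s0·½·√(1/n1 + 1/n2); 40 df (t = 2.0211).
- Shift of the unadjusted estimate: π·(n1 − n2)/N.

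**Worked case, 21:21, π = 300, r = 0.5.** Unadjusted SD = √(917² + 300²·42/41) = 966 kcal, standard error 149.05, half-width 2.0195 × 149.05 = 301.0 kcal. Adjusted half-width = 2.0211 × 141.5 = 286.0 kcal. The ratio is 1.053.

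| π (kcal) | Unadjusted half-width, 21:21 | Wider than 286.0 by, r = 0.5 | r = 0 | r = 0.7 | Shift at 22:20 | Shift at 23:19 |
|---|---|---|---|---|---|---|
| 100 | 287.5 | 0.5% | 0.2% | 0.9% | 5 | 10 |
| 200 | 292.6 | 2.3% | 1.1% | 3.9% | 10 | 19 |
| 300 | 301.0 | 5.3% | 2.6% | 8.7% | 14 | 29 |

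The percentages for r = 0 and r = 0.7 are relative to the adjusted half-width at that correlation. With r = 0.5 and π = 300, an SD of 600 or 1,200 kcal for the other app gives 6.8% or 3.8%.

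**Size of the shift.** At 23:19 and r = 0.5 it is 0.07 to 0.19 of the unadjusted standard error (142 to 149 kcal).

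**Type I error and power** (200,000 simulated trials, 21:21, r = 0.5). For π = 100, 200 and 300, unadjusted type I error is 0.049, 0.045 and 0.039. Power for a 406 kcal difference is 0.80, 0.79 and 0.77, against 0.80 adjusted.

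**When adjustment does not pay.** Equating the two half-widths at r = 0.5 gives a break-even π of 35 kcal at 21:21, 56 at 22:20 and 94 at 23:19. With π = 0 the adjusted interval is wider by 0.08%, 0.19% and 0.53% at those splits. At 23:19 with π = 100 the gain is only 0.07%.

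**How likely unequal orders are.** The plan says "We expect no more than ~8% drop-out and will recruit at least 45 participants". If counterbalancing gives 23:22 and three drop out regardless of order, the hypergeometric probabilities are 39% for 21:21, 50% for 22:20 either way and 11% for 23:19. The shift then averages close to zero.

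**Choice of adjusted method.** With complete pairs, the mixed model with app and period gave the same app estimate as the equal-weight mean of the two order-specific means (141.677 for both in a simulated 23:19 data set). With three participants leaving after Period 1 they no longer agree, because the mixed model uses the single periods and the t-test cannot. Two small simulations gave mean differences between the methods of about 14 and 16 kcal (up to 58), against about 7 and 10 kcal between the adjusted and unadjusted paired estimates.

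**The case against.** The strongest reply is that nothing needs mending. Counterbalancing already deals with period bias except through chance or differential dropout, expected dropout is small, and each period has its own training and run-in. The t-test does not inflate false positives. The comparison is exploratory, and every gain above rests on an assumed period effect. The largest shift needs both the largest assumed effect and a split with 11% probability. All of this stands, and it is why the point is only an improvement.

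It does not remove the point. Adjustment is the standard crossover analysis, period is known by design, and the downside is bounded and small.

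A reader might go further and infer that learning carries over and invalidates the comparison. The documents do not show this. The training covers portion estimation, and the section on potential benefits says only that awareness of portion sizes might improve. Error is signed and measured against weighed intake, so practice could reduce its spread without moving its mean.

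**Conclusion.** A minor, inexpensive improvement. Under the assumptions listed, the unadjusted interval is 0.5% to 5.3% wider at 21:21 for period effects of 100 to 300 kcal and r = 0.5, and the estimate moves by at most 29 kcal (0.19 standard errors) at 23:19. Below the break-even effect the adjusted interval is the wider one, though only slightly.

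Two stronger readings are not supported. One is that the planned t-test is wrong or biased: with balanced orders it is unbiased, and its type I error falls below 0.05. The other is that the study's main conclusions are at risk: the primary equivalence tests compare each app with weighed intake, do not use this test, and keep their stated power.

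**What to change.** In Outcome measures, replace the dependent samples t-test between apps with the period-adjusted crossover t-test. Its estimate is the equal-weight mean of the two order-specific mean paired differences in error, with a pooled within-order variance on 40 degrees of freedom if 42 complete. State that the analysis set is participants who complete both periods, and label the comparison exploratory so that it matches Power calculation.

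Name this one method only. A mixed model should not be listed as an equivalent option, because the two agree only with complete pairs. Leaving both open would allow a choice that can change the estimate by more than the adjustment itself does.

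The change is to wording, with no new data. It costs one degree of freedom (40 instead of 41) and, if there is no period effect, up to about 0.5% of interval width at splits up to 23:19.
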